### **4.3 Pharmacokinetic Set**

The Pharmacokinetic (PK) Set will consist of subjects who receive at least 1 dose of study drug and have evaluable post-dose maribavir PK data (defined as complete concentration-time profile to obtain meaningful estimates of PK parameters). The PK analyses will be based on this analysis set.

Subjects who do not provide reliable concentration-time profile (in 1 or more periods) may be excluded from PK analysis (for the corresponding treatment period).

## 5. STUDY SUBJECTS

### 5.1 Disposition of Subjects

The number of subjects who were included in each defined statistical analysis set (Enrolled, Safety, and PK) will be summarized by cohort and overall.

Summaries and listing of subject disposition will be based on the Enrolled Set.

The reasons for exclusion from the PK set will be presented in the listings with details of any AEs.

The number and percentage of subjects who completed and prematurely discontinued the study, as well as subjects who completed dosing and prematurely discontinued the study drug, as recorded on the termination page of the electronic case report form (eCRF), will be presented for each cohort and overall for the Safety Set. Reasons for premature discontinuation from the study, as well as discontinuation from study drug, as recorded on the termination page of the eCRF will be summarized (number and percentage) by cohort and overall, for the Safety Set. All subjects who prematurely discontinued the study and/or discontinued the study drug will be listed by discontinuation reason.

### 5.2 Demographic and Other Baseline Characteristics

Descriptive summaries of demographic and baseline characteristics will be presented by cohort and overall, for the Safety Set as well as the PK Set. Demographics and other baseline characteristics data will be listed for the Safety Set.

The following demographic characteristics will be summarized in the following order in the tables: age (years), sex, race, and ethnicity. The following baseline characteristics will be summarized in the following order in the baseline table: weight (kg), height (cm), and body mass index (BMI, kg/m^2).

Age, sex, race, and ethnicity will be summarized based on data obtained at the Screening Visit. Height and weight will be summarized from the last available measurement prior to the first single dose of IP, and BMI will be calculated.

Age will be calculated as the integer part of: (date of informed consent is signed – date of birth + 1)/365.25. Body mass index will be calculated using the following formula: weight (kg) / (height [m]).

### 5.3 Medical History

Medical history will be collected at the Screening Visit and will be coded using agreed upon MedDRA Version 23.0 or newer. Listings will be provided using the Safety Set.

Medical history will be summarized by system organ class (SOC) and preferred term (PT) for each cohort, based on the Safety Set. The summary of medical history will include the number

and percentage of subjects who experienced the event and number of events experienced. System organ class will be sorted alphabetically, and within each SOC, PT will be sorted in the table Total column by descending order of frequency.

#### **5.4 Prior Medications (Therapies), and Procedures**

All prior medications, therapies, and procedures will be listed based on the Safety Set. Prior medications will be coded using the World Health Organization Drug Dictionary Global B3 dated March 2020.

Prior medications (therapies) and procedures are defined as the medications (therapies) and procedures with a start date prior to the date of the first single dose of IP.

Prior medication usage presented by therapeutic class according to Anatomical Therapeutic Chemical (ATC) classification and PT will be summarized based on the number and proportion of subjects in each cohort and in overall subjects based on the Safety Set. Multiple medication usage by a subject in the same category will be counted only once.

#### **5.5 Concomitant Medications (Therapies) and Procedures**

Concomitant medications will be coded using the World Health Organization Drug Dictionary Global B3 dated September 2019.

Medications (therapies) and procedures taken during the study will be considered concomitant to the treatment(s) a subject has taken during the duration of the medications. Medications with start and stop dates and times during the wash-out period or the 7 days follow-up period after last single dose of IP will be considered concomitant to the prior treatment(s) subject received. Any medication/therapy and procedure with a start date and time after 7 days following the date and time of the last single dose of IP will be considered post-treatment medication/therapy and procedure and not be considered a concomitant medication/therapy and procedure.

Concomitant medication usage presented by therapeutic class (according to Anatomical Therapeutic Chemical classification) and PT will be summarized based on the number and proportion of subjects by cohort, treatment group and overall, based on the Safety Set. Multiple medication usage by a subject in the same category will be counted only once.

All concomitant therapies, procedures and medication will be listed for the Safety Set.

#### **5.6 Exposure to Investigational Product**

Exposure to the IP (maribavir) will be summarized in terms of total planned dose in mg. Descriptive statistics (n, mean, standard deviation [SD], minimum, median, and maximum) will be presented to describe the exposure to IP by cohort and treatment group based on the Safety Set.

Listings will be created by subject number and visit presenting the date and time of dose administration separately based on the Safety Set.

## **5.7 Measurements of Treatment Compliance**

Treatment compliance will be summarized in terms of number of subjects who completed the drug administration, who fasted 10 hours before the investigational drug administration, and who fasted 4 hours after the investigational drug administration, by cohort and treatment group based on the Safety Set.

## **5.8 Protocol Deviations**

Protocol deviations will be recorded by the site separately from the clinical database using a Protocol Deviation tracker. Protocol deviations will be classified as major or minor per the agreed protocol deviation management plan and will be documented in the Protocol Deviation tracker. The Sponsor study team will review the protocol deviations and their classification throughout the study and before database lock.

Major/minor protocol deviations will be summarized by category for each cohort, each treatment group, and overall based on the Safety Set. Major/minor protocol deviations will be listed based on the Safety Set.

## 6. EFFICACY ANALYSES

Not applicable.

## 7. SAFETY ANALYSIS

The safety analysis will be performed using the Safety Set. Safety variables include AEs, vital signs, ECG, and clinical laboratory variables. For each safety variable, the last value collected before the first dose of investigational product will be used as baseline for all analyses of that safety variable. Last Value on Treatment (LVOT) will be defined as the last valid assessment obtained after Baseline and until 7 days after last dose of investigational product.

All safety analyses will be conducted according to the treatment the subject actually received.

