8.8 Safety Analyses

The Safety Set will be used to summarize safety data. Safety will be assessed for the following evaluations:

- Number, severity, seriousness, and causality of TEAEs
- Changes in vital signs ECGs, and clinical laboratory results (hematology, chemistry, and urinalysis) from baseline to post-baseline time points. Baseline is defined as the last non-missing assessment prior to the first dose.

Safety data, including TEAEs, 12-lead ECGs, vital signs (systolic and diastolic blood pressure, pulse rate, respiratory rate), and clinical laboratory data (biochemistry, hematology, and urinalysis), will be summarized with the descriptive statistics. Potentially clinically important findings will also be summarized or listed. The potentially clinically important values will be defined in the SAP.

Quantitative safety data as well as the difference from baseline, if applicable, will be summarized by descriptive statistics. Frequency counts will be compiled for classification of qualitative safety data. Direct safety comparisons between the two cohorts (the subjects of Japanese descent and Non-Hispanic Caucasian subjects) will be presented from the maribavir 400 mg dosing data. All other safety data from the 200 mg and 800 mg in the subjects of Japanese descent will be summarized and listed.

For each safety variable, the last value collected before the first dose of investigational product in that treatment period will be used as baseline for all analyses of that safety variable in that treatment period.

An AE (classified by preferred term [PT]) that occurred during the study will be considered a TEAE if it had a start date on or after the first dose of investigational product or if it had a start date before the date of the first dose of investigational product, but increased in intensity on or after the date of the first dose of investigational product. An AE that occurred after the follow-up phone call will not be counted as a TEAE.

Adverse events will be coded using the agreed-upon version of Medical Dictionary for Regulatory Activities, Version 23.0. or later. The number of events, incidence, and percentage of TEAEs will be calculated overall, by system organ class, and by PT. Treatment emergent adverse events will be further summarized by severity and relationship to investigational product. Adverse events related to investigational product, AEs leading to withdrawal, SAEs, and deaths will be similarly summarized/listed.

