### 2.2.2 Exploratory Pharmacokinetic Endpoints

### 2.2.3 Safety Endpoints

The safety analysis will be performed using the Safety Analysis Set. Safety endpoints include AEs, vital signs, ECG variables, and clinical laboratory variables. The following safety evaluations will be performed:

- Number, severity, seriousness, and causality of treatment-emergent adverse events (TEAEs).
- Changes in vital signs, ECGs, and clinical laboratory results (hematology, chemistry, and urinalysis) from baseline to post-baseline time points.

For each safety variable, the last value collected before the first dose of investigational product in that period will be used as baseline for all analyses of that safety variable in that period.

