#### 7.4 Electrocardiogram (ECG)

Descriptive statistics for ECG variables (eg, heart rate, PR interval, RR interval, QRS interval, QT interval, and QTc interval) and their changes from baseline at each assessment time point will be presented by cohort and treatment group. QTc interval will be calculated using both Bazett ( $QTcB=QT/(RR)^{1/2}$ ) and Fridericia ( $QTcF=QT/(RR)^{1/3}$ ) corrections; and if RR is not available, it will be replaced with 60/hr in the correction formula. ECG interpretation will be summarized by visit. A shift table from baseline to each visit for qualitative ECG results will be presented. If the QTcF interval is increased by >45 msec from the baseline, or an absolute QTcF value is >500 msec for any scheduled ECG, then ECG should be repeated 2 more times and the average of the 3 QTc values will be recorded in the CRF and used to generate descriptive summary.

Electrocardiogram variable values will be considered PCS if they meet or exceed the normal limit values listed in Table 3. The number and percentage of subjects with post-baseline PCS values will be tabulated by cohort and treatment group. The percentages will be calculated relative to the number of subjects with available non-PCS baseline and at least 1 post-baseline assessment. The numerator is the total number of subjects with at least 1 PCS post-baseline ECG value. A listing of all subjects with post-baseline PCS value will be provided including the subject number, baseline, and post-baseline PCS values.

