### 12.2 Repeated or Unscheduled Assessments of Safety Parameters

If a subject has repeated assessments before the start of investigational product, then the results from the final assessment made prior to the start of investigational product will be used as baseline. If end of study assessments are repeated or unscheduled, the last post-baseline assessment will be used as the end of study assessment for generating descriptive statistics. If there are repeated assessments at other post-baseline timepoints, the assessment from scheduled visit will be considered for summarizing data. However, all post-baseline assessments will be used for PCS value determination and all assessments will be presented in the data listings.

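### SAP Sections 7 and 2.2.3 set different safety baselines for the 200 mg and 800 mg data, and nothing says which applies

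*SAP*

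**What the plan says.** SAP Section 7, which governs the safety tables, states that "the last value collected before the first dose of investigational product will be used as baseline for all analyses of that safety variable". SAP Section 2.2.3 has nearly the same sentence with a period qualifier: "the last value collected before the first dose of investigational product in that period will be used as baseline".

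Protocol Section 8.8 carries both versions. It first says "Baseline is defined as the last non-missing assessment prior to the first dose", and later "the last value collected before the first dose of investigational product in that treatment period will be used as baseline". The protocol synopsis gives only the study-level version.

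SAP Section 12.2 says of repeated assessments that "the results from the final assessment made prior to the start of investigational product will be used as baseline". It does not say whether the start is that of the study or of the period. SAP Section 14 lists a single change from the protocol, about the Safety Set, and is silent on baseline.

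Three other rules depend on the definition:
- ECG PCS percentages in SAP 7.4 use as denominator the "number of subjects with available non-PCS baseline and at least 1 post-baseline assessment".
- SAP 12.2 says that "all post-baseline assessments will be used for PCS value determination".
- SAP 7 defines the last value on treatment as "the last valid assessment obtained after Baseline and until 7 days after last dose of investigational product".

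**The concern.** Every subject receives 400 mg in Period 1. Japanese subjects then receive 200 mg and 800 mg in Periods 2 and 3, in randomised order. A study-level baseline therefore measures changes after 200 mg or 800 mg from a value taken before a different dose, with one or two earlier doses in between.

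SAP 7 is hard to read as period-specific. SAP 7.1, which follows it directly, refers to the first dose in the same way to mark the start of treatment emergence for the whole study. Two programmers could each follow the SAP and produce different tables.

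The affected tables report a stated secondary objective, the safety and tolerability of 200 mg and 800 mg in Japanese subjects. The study is open-label, so the rule should be fixed before anyone can see how the two versions differ.

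**Working it through.** The plan states no figure on this point, so there is none to reproduce. The check compares the rules against the schedules and counts what depends on them.

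**1. Where the rules differ.** Planned subject-periods are 12 × 3 (Japanese) + 12 × 1 (Caucasian) = 48. In Period 1 (400 mg) both rules pick the same value: 12 + 12 = 24 subject-periods. In Periods 2 and 3 they pick different values: 12 × 2 = 24 subject-periods, all at 200 mg or 800 mg.

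**2. What the difference contains.** Let *B*₁ be the Period 1 predose value, *B*ₖ the predose value of period *k* (2 or 3), and *Y* a post-dose value in period *k*.
- Study-level change: *Y* − *B*₁
- Period change: *Y* − *B*ₖ
- Difference: *B*ₖ − *B*₁

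The difference arises before the dose under assessment but would be reported under that dose. With doses 72 to 73 hours apart, *B*₁ lies about 72 hours (Period 2) or 144 hours (Period 3) before that dose. Under Protocol Tables 3 and 4, *B*ₖ lies at most 30 minutes before it for blood samples and 60 minutes for vital signs and ECG.

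An illustration with assumed values: a woman has QTcF 420 msec at Period 1 predose, 435 at Period 2 predose and 452 after the Period 2 dose. SAP Table 3 requires more than 450 and an increase of more than 30. The study-level change is 452 − 420 = 32, which is flagged. The period change is 452 − 435 = 17, which is not.

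**3. PCS criteria that use change from baseline.** Each parameter-by-direction row of SAP Tables 1 to 3 was counted, leaving out the three NA rows.

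| Table | Rows | Rows using change | Which |
|---|---|---|---|
| 1, haematology | 18 | 2 | haemoglobin low, haematocrit low |
| 1, biochemistry | 33 | 11 | potassium 2, creatinine 1, calcium 2, protein 2, albumin 2, uric acid 2 |
| 1, urinalysis | 7 | 0 | none |
| 2, vital signs and weight | 12 | 8 | systolic 2, diastolic 2, heart rate 2, weight 2 |
| 3, ECG | 7 | 5 | heart rate 2, PR 1, QTc 2 |
| Total | 77 | 26 | |

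Other conventions change the count little:
- 27 of 77 if total bilirubin is counted by its label rather than its criterion.
- 26 of 80 with the NA rows included.
- 28 of 79 with the Bazett and Fridericia corrections counted separately.
- 26 of 73 if the four TSH and free T4 rows are dropped, because inclusion criterion 6 limits those tests to screening.

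The other two ECG rows (overall evaluation and QRS) depend on baseline through the SAP 7.4 denominator.

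**4. Which values count as post-baseline.** Under the study-level rule, the predose values of Periods 2 and 3 become post-baseline values, and SAP 12.2 would use them for PCS. Scheduled post-baseline assessments in the 12 Japanese subjects are:

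| | Period rule | Study-level rule |
|---|---|---|
| Laboratory | 3 × 12 = 36 | 5 × 12 = 60 |
| Vital signs (excluding weight) | 6 × 12 = 72 | 8 × 12 = 96 |
| ECG | 6 × 12 = 72 | 8 × 12 = 96 |
| Weight | 1 × 12 = 12 | 3 × 12 = 36 |

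In each row the extra 24 values are the Period 2 and 3 predose measurements. No text says which dose they belong to. The 12 taken before the Period 2 dose follow the 400 mg dose, so the 400 mg safety comparison is largely, but not wholly, free of the problem.

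**The case against.** The best defence is that a usable rule already exists. The period-specific definition appears in both documents, is the more specific of the two, and matches a schedule that collects predose vital signs, ECG and laboratory tests in every period. On that view SAP 7 has merely lost a few words. This is a fair account of what was probably intended, and it points to the right correction. It does not remove the conflict: no text gives the specific rule priority, and SAP 7 applies its rule to all analyses.

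The second argument is that the consequences are small. The outputs are descriptive, the direct cohort comparison uses 400 mg data, and all assessments are listed, so either change can be recomputed. With the half-life of 5 to 7 hours in Protocol Section 1.2.3, a 72-hour washout covers 72/7 ≈ 10 to 72/5 ≈ 14 half-lives, so little residual drug is expected at the next predose. All of this stands, and it limits the weight of the point. Washout does not exclude other drift between periods, such as effects of confinement, repeated blood draws or ordinary within-subject variation.

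It is also true that a count of rows measures dependence on the wording, not the number of flags that would change. In addition, no output in SAP 7.1 to 7.4 uses the last value on treatment, so redefining it is secondary.

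**Conclusion.** The concern holds. SAP 7 and SAP 2.2.3 give incompatible baselines for all 200 mg and 800 mg safety data (24 of 48 planned subject-periods), and nothing in either document resolves it. Change summaries, laboratory and ECG shift tables, and 26 of 77 PCS criteria are directly affected. The remaining criteria can be affected only through denominators or through which values count as post-baseline.

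The counts assume full enrolment and completion of the scheduled assessments, and the row convention stated above. No effect on results is claimed, because the documents give no figure for predose differences between periods. The point should be corrected before database lock. It does not threaten the primary pharmacokinetic analysis.

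**What to change.** Amend SAP 7 to the rule already in SAP 2.2.3 and Protocol 8.8: baseline is the last non-missing value before dosing in that treatment period, for changes, shifts and PCS flags. Then:

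1. In SAP 12.2, state that the start of investigational product means the dose in that period.
2. State that Period 2 and 3 predose values are the baseline of that period and not post-baseline values of the previous treatment. Also say what happens when that predose value is missing, in particular whether a post-dose value from the previous period may stand in for it.
3. Give weight its own rule, because Japanese subjects have a scheduled post-dose weight only in Period 3. One option is a single change from Period 1 predose to Period 3 Day 2, reported by cohort and not by dose.
4. If the last value on treatment is kept, define it by period: after that period's dose and before the next dose or, for the last dose, up to 7 days after it.
5. Record the choice in SAP 14, so that the study-level sentence in Protocol 8.8 and the synopsis is visibly set aside.

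The first two items and the SAP 7 edit are the core; the others close gaps that would remain. The cost is SAP wording and a programming specification before database lock. No new data are needed, and no protocol amendment for this alone.

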### 7.1 Adverse Events

Adverse events will be coded using MedDRA Version 23.0 or newer.

An AE (classified by preferred term) that occurs during the study will be considered a TEAE if it has a start date on or after the first dose of investigational product or if it has a start date before the date of the first dose of investigational product, but increases in severity on or after the date of the first dose of investigational product. If more than 1 AE with the same preferred term is reported before the date of the first dose of investigational product, then the AE with the greatest severity will be used as the benchmark for comparison to the AEs occurring during the study under the preferred term. Adverse events during the study will be assigned to the treatment(s) a subject has taken at the onset of the event. An AE with start date and time during the wash-out period or the 7 days follow-up period after last single dose of IP will be assigned to the prior treatment subject received. An AE that occurs more than 7 days after the date of the last dose of investigational product will not be counted as a TEAE.

An overall summary of the number of subjects with TEAEs as well as the number of events will be presented, including the number and percentage of subjects with any TEAEs, serious TEAEs, TEAEs related to investigational product and TEAEs leading to discontinuation of investigational product.

The number and percentage of subjects reporting TEAEs, as well as the number of events, in each cohort, each treatment group, and overall will be tabulated by system organ class (SOC) and preferred term (PT); by SOC, preferred term (PT), and maximum severity. TEAEs considered related to investigational product will also be summarized by SOC and preferred term. If more than 1 AE occurs with the same preferred term for the same subject, then the subject will be counted only once for that preferred term using the most severe and most related occurrence for the summarization by severity and by relationship to investigational product. Presentation by SOC and PT will present SOC sorted alphabetically and PT within SOC by descending incidence.

TEAEs and related TEAEs will be summarized by preferred term by descending frequency. Serious TEAEs, TEAEs leading to discontinuation of investigational product and serious TEAEs leading to death, will be summarized by SOC, preferred term, cohort, and treatment group.

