7.2.2 Safety

The name and address of each third party vendor (eg, clinical laboratory) used in this study will be maintained in the investigator's and sponsor's files.

Actual safety assessment times will be monitored and recorded. The sponsor's expectation is that the investigator will ensure that every effort is made to perform all assessments at the protocol-scheduled time. Any safety assessment that deviates from the scheduled assessment time set forth in the protocol by more than ± 15 minutes will be considered a protocol deviation.

Adverse events (defined as AEs occurring from the time of informed consent signature to first dose of IP), TEAEs (all AEs occurring after the first treatment or worsening after the first treatment), prior medication, and concomitant medication use will be assessed and monitored from the time the subject signs the informed consent form to completion of study (including to time of screen failure or dropout/discontinuation). While confined in the CRC, subject safety will also be closely monitored through blood pressure measurements, ECG measurement, clinical safety labs, and physician oversight.

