Appendix 2.1 Adverse Event Definitions

An AE is any untoward medical occurrence in a clinical investigation subject administered a pharmaceutical product and that does not necessarily have a causal relationship with this IP or medicinal product. An AE can therefore be any unfavorable and unintended sign (including an abnormal laboratory finding), symptom, or disease temporally associated with the use of a medicinal (investigational) product, whether or not related to the medicinal (investigational) product (ICH Guidance E2A 1995).

Treatment-emergent Adverse Event

A TEAE is defined as any event emerging or manifesting at or after the initiation of treatment with an IP or medicinal product or any existing event that worsens in either intensity or frequency following exposure to the IP or medicinal product.

Serious Adverse Event

An SAE is any untoward medical occurrence (whether considered to be related to IP or not) that at any dose:

- Results in death
- Is life-threatening. Note: The term ‘life-threatening’ in the definition of “serious” refers to an event in which the subject was at risk of death at the time of the event; it does not refer to an event which hypothetically might have caused death if it was more severe.
- Requires inpatient hospitalization or prolongation of existing hospitalization. Note: Hospitalizations, that are the result of elective or previously scheduled investigations procedures or surgery for pre-existing conditions and have not worsened after initiation of treatment, should not be classified as SAEs. For example, an admission for a previously scheduled ventral hernia repair would not be classified as an SAE; however, complication(s) resulting from a hospitalization for an elective or previously scheduled surgery that meet(s) serious criteria must be reported as SAE(s).
- Results in persistent or significant disability/incapacity
- Results in a congenital abnormality/birth defect

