### **12.3.3 Missing Severity Assessment for Adverse Events**

If severity is missing for an AE starting prior to the date of the first dose of IP, then a severity of “Mild” will be assigned. If the severity is missing for an AE starting on or after the date of the first dose of IP, then a severity of “Severe” will be assigned. The imputed values for severity assessment will be used for incidence summaries, while both the actual and the imputed values will be used in data listings.

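### TEAEs are classified by start date without clock time, so an AE that begins on Day 1 before the first dose can count as treatment-emergent and then has no treatment column

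*SAP*

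**What the plan says.** **Statistical definition.** SAP 7.1 has two limbs. A new event is "considered a TEAE if it has a start date on or after the first dose of investigational product". An older event qualifies "if it has a start date before the date of the first dose of investigational product" and its severity then increases on or after that date. Protocol 8.8 uses the same first limb: "considered a TEAE if it had a start date on or after the first dose of investigational product". Neither mentions clock time.

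**Clinical definition.** Protocol 7.2.2 describes "TEAEs (all AEs occurring after the first treatment or worsening after the first treatment". Protocol Appendix 2.1 describes "any event emerging or manifesting at or after the initiation of treatment with an IP". Both are anchored to treatment, not to the calendar day.

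**Allocation to treatment.** SAP 7.1: "Adverse events during the study will be assigned to the treatment(s) a subject has taken at the onset of the event". For events between doses the SAP does use clock time: "An AE with start date and time during the wash-out period or the 7 days follow-up period" goes to the previous treatment.

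**Related rules that use the date.** When several pre-dose AEs share a preferred term, SAP 7.1 takes as severity benchmark the worst of those reported before the date of first dose. SAP 12.3.3 sets severity to severe "If the severity is missing for an AE starting on or after the date of the first dose of IP", and SAP 12.3.4 sets a missing relationship to related by the same test.

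**The concern.** Every subject passes the first hours of Day 1 undosed, after an overnight fast. Protocol Tables 2 and 6 schedule AE collection at the predose time point of that day in both cohorts. An event that starts then carries the calendar date of the first dose, so a date comparison calls it treatment-emergent although no drug has been given. That conflicts with two of the protocol's own definitions, and two programmers working faithfully from the documents could produce different TEAE tables.

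Only the first dose is exposed. Before the second and third doses, the date-and-time rule sends events to the prior treatment. The first dose is 400 mg in both cohorts. The imputation rules add to the problem: a pre-dose Day 1 event with missing severity or causality would be tabulated as severe or related.

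**Working it through.** The documents give no figure to reproduce on this point: no AE rate, and a sample size justified by feasibility. The check is a comparison of rules, followed by arithmetic for scale.

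**1. Follow one event through the rules.** Take an AE that starts on Day 1 of Period 1 before dosing.

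| Rule | Result |
|---|---|
| SAP 7.1 and Protocol 8.8, first limb, read by date | TEAE |
| SAP 7.1 and Protocol 8.8, first limb, read by time | Not a TEAE |
| SAP 7.1, worsening limb | Not covered: start date is not before the first-dose date |
| SAP 7.1, severity benchmark | Not used, for the same reason |
| Protocol 7.2.2 and Appendix 2.1 | Not a TEAE unless it worsens after dosing |
| SAP 7.1, allocation | No treatment taken at onset, so no column |
| SAP 12.3.3 and 12.3.4, if the value is missing | Severe; related |

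The two limbs cover all AEs without a gap only if both are read by date. If the first limb is read by time, a pre-dose Day 1 event that worsens after dosing falls in neither. Protocol Appendix 2.3 softens this, because it records a change in severity as a new event.

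**2. Repeat for Periods 2 and 3.** A pre-dose event there falls in the washout, is tested by date and time, and goes to the prior dose. There is no ambiguity.

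**3. Size per subject.** Inputs: 12 subjects per cohort, 24 in total (SAP 3.1).
- One subject in a cohort column: 100 × 1/12 = 8.33 percentage points.
- One subject in the overall column: 100 × 1/24 = 4.17 points.

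These are upper limits. The shift occurs only if the subject is not already counted in that row, and for a dose column only if the event is placed there.

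**4. How often.** The documents give no rate of pre-dose AEs. Let p be the assumed probability that a subject has a Day 1 pre-dose AE, independently across subjects. The expected number per cohort is 12p, and the chance of at least one affected subject among n is 1 − (1 − p)^n.

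| p (assumed) | Expected per 12 | At least one of 12 | At least one of 24 |
|---|---|---|---|
| 0.5% | 0.06 | 5.8% | 11.3% |
| 1% | 0.12 | 11.4% | 21.4% |
| 2% | 0.24 | 21.5% | 38.4% |
| 5% | 0.60 | 46.0% | 70.8% |
| 10% | 1.20 | 71.8% | 92.0% |

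The table shows sensitivity to the assumption. It is not an estimate of what will happen.

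**The case against.** The best defence is that the first limb refers to the first dose, not to its date, and can be read by time. SAP 12.3.2 helps that reading: it asks when the event occurred relative to drug administration. The SAP also presents itself as an elaboration of the protocol, whose Section 7.2.2 and Appendix 2.1 give the post-treatment meaning. This stands in part. The fault is an unspecified test, not a rule that certainly captures pre-dose events. It does not remove the point, because the worsening limb, the benchmark and both imputation rules name the date explicitly.

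A reader might infer that the rule inflates the 400 mg columns. The documents do not support that as an established result. The allocation rule gives the event no dose column, and placing it under 400 mg needs a programming default that is nowhere stated.

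A reader might also infer bias in the Japanese versus Caucasian safety comparison. No mechanism for that is shown: both cohorts take 400 mg first under the same rule, predose AE collection and fast. Only chance imbalance remains.

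Other mitigating points are fair:
- The extra window is short beside those the SAP already sets. If dosing is at 08:00 (an assumption), 400 mg collects about 8 + 72 = 80 hours, against about 72 hours for the Period 2 dose and 7 × 24 = 168 hours for the Period 3 dose.
- Many subjects may already have a TEAE. Protocol 1.2.5 reports dysgeusia in up to 80% of subjects in single-dose studies.
- Treatment emergence is a statement about timing. The investigator judges causality separately, and SAP 12.3.3 and 12.3.4 list actual beside imputed values.
- The safety summaries are descriptive, and counting same-day events errs on the cautious side.

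These limit the consequence but do not resolve the conflict between the definitions.

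**Conclusion.** The point holds as a correctable defect of small expected effect. As written, an AE that starts on Day 1 before the first dose can be counted as treatment-emergent, against Protocol 7.2.2 and Appendix 2.1, and SAP 7.1 then gives it no treatment column. Under date-level programming it enters the overall TEAE count. If a default also puts it under 400 mg, the comparison of 400 mg with 200 and 800 mg in the Japanese cohort is exposed in one direction, because the other two doses have no such window.

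The size is at most 8.3 points in a 12-subject column and 4.2 points in the total of 24, per subject whose only TEAE is such an event. The number of such subjects is unknown. The conclusion rests on the date-level reading of the first limb, which is the natural one to program but not the only one possible.

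**What to change.** In SAP 7.1, define a TEAE as an AE whose start date and time are at or after the date and time of the first dose, or which worsens after that time. Where onset time is missing, use the date alone and count a Day 1 event as a TEAE; this fits the default in SAP 12.3.2. Apply the same test to the worsening limb, the severity benchmark, and the imputation rules in SAP 12.3.3 and 12.3.4. Reconcile Protocol 8.8 with Protocol 7.2.2 and Appendix 2.1.

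The cost is wording only, with no change to design or sample size. Dosing time is already captured in the CRF (Protocol 6.5). The one dependency is AE onset time: Protocol Appendix 2.3 speaks of start and stop dates, and no section states that the CRF records the time. SAP 7.1 already presumes it for washout events, so this should be confirmed against the CRF before the SAP is revised.
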